### **Other exclusions**

- 42a. The study participant must not ingest grapefruit, starfruit, or pawpaw (as beverage, fruit or supplements) within 72 hours before the study medication administration or be under treatment with any known strong CYP3A4 inhibitor or inducer within 72 hours before study drug administration or throughout the entire study period (Section 6.5.2).
- 43a. Vulnerable participants (eg, participants kept in detention, soldiers, adults with legally authorized representative, employees of the Sponsor or the CRO with direct involvement in the proposed study or other studies under the direction of the Investigator or the CRO, as well as family members of the employees or the Investigator. In France, another example of vulnerable participants includes participants who do not benefit from social security schemes such as health insurance. (For specific requirements in France, please refer to Section 10.9, Appendix 9.)
- 44. A female study participant who tests positive for pregnancy, plans to get pregnant during the participation in the study, or who is breastfeeding.
- 45. Study participant with hypokalemia, defined as a serum potassium level below the lower limit of the laboratory's reference range.

## **5.3 Lifestyle restrictions**

### **5.3.1 Meals and dietary restrictions**

The study participant must not ingest grapefruit, starfruit, or pawpaw (as beverage, fruit or supplements) within 72 hours before the study medication administration and throughout the study.

### **5.3.2 Caffeine, alcohol, and tobacco**

There are no restrictions for caffeine or tobacco during the study. Prior documentation of alcohol abuse is an exclusion criterion, and study participants are requested to practice only moderate alcohol consumption.

### **5.3.3 Activity**

There are no restrictions on any activities.

## **5.4 Screen failures**

Screen failures are defined as participants who consent to participate in the clinical study but are not subsequently randomly assigned to study medication. A minimal set of screen failure information is required to ensure transparent reporting of screen failure participants to meet the Consolidated Standards of Reporting Trials publishing requirements and to respond to queries

---

from regulatory authorities. Minimal information includes demography, screen failure details, eligibility criteria, and any serious adverse event (SAE).

For study participants otherwise fully eligible but not able to be randomized as planned for personal reasons, rescreening may be allowed once per participant at the discretion of the Investigator, following discussion with the Medical Monitor. If Visit 2 was completed during screening, only Visit 1 needs to be completed for rescreening. However, the maximum period between DaT-SPECT, MRI assessment, and V1 need to be adhered to as per inclusion criteria. Rescreened participants will be assigned a new participant number.

Rescreening in case of abnormal laboratory results can be considered only in case of test results for which there are strong reasons to be considered transitory and/or without clinical safety significance. In these cases, the assessments might be repeated after consultation with the Medical Monitor.

## **6 STUDY TREATMENTS/INVESTIGATIONAL DEVICE**

Study treatment is defined as any investigational treatment(s), marketed product(s), placebo, or medical device(s) intended to be administered to a study participant according to the study protocol.

## 6.1 Treatments administered

ARM Name	UCB0599 180mg/day	UCB0599 360mg/day	Placebo
Intervention name	UCB0599	UCB0599	Placebo
Type	Drug	Drug	Placebo
Dose formulation	Granules in capsules and matching placebo capsules	Granules in capsules	Matching placebo capsules
Unit dose strength(s)	90mg and 0mg	90mg	0mg
Dosage level(s)a	180mg/day [90mg BID]	360mg/day [180mg BID]	NA BID intake
Route of administration	Oral – 2 capsules 90mg and 2 matching placebo capsules per day BID approximately 12 hours apart	Oral – 4 capsules 90mg per day BID approximately 12 hours apart	Oral – 4 matching placebo capsules per day BID approximately 12 hours apart
Use	Experimental	Experimental	Placebo-comparator
IMP and NIMP	IMP	IMP	IMP
Sourcing	IMP will be supplied by UCB Clinical Trial Supply or designee.	IMP will be supplied by UCB Clinical Trial Supply or designee.	IMP will be supplied by UCB Clinical Trial Supply or designee.
Packaging and labeling	UCB0599 and placebo capsules are manufactured, packaged, and labeled according to Good Manufacturing Practice guidelines and applicable laws or regulations.	UCB0599 and placebo capsules are manufactured, packaged, and labeled according to Good Manufacturing Practice guidelines and applicable laws or regulations.	UCB0599 and placebo capsules are manufactured, packaged, and labeled according to Good Manufacturing Practice guidelines and applicable laws or regulations.
Current/Former name(s) or alias(es)	NA	NA	NA

BID=twice per day. IMP=investigational medicinal product; NA=not applicable

a Participants will be randomized to either UCB0599 360mg/day (180mg BID), UCB0599 180mg/day (90mg BID), or placebo to achieve a final randomization ratio of 1:1:1 when the IMP for low dose UCB0599 180mg/day (90mg BID) will be available to supply sites.

## 6.2 Preparation, handling, storage, and accountability requirements

The Investigator or designee must confirm appropriate temperature conditions have been maintained during transit for all study medication received and any discrepancies are reported and resolved before use of the study medication.

Only participants enrolled in the study may receive study medication, and only authorized site staff may supply or administer study medication. All study medications must be stored in a

secure, environmentally controlled, and monitored (manual or automated) area in accordance with the labeled storage conditions with access limited to the Investigator and authorized site staff.

The Investigator, institution, or the head of the medical institution (where applicable) is responsible for study medication accountability, reconciliation, and record maintenance (ie, receipt, reconciliation, and final disposition records).

In case an out-of-range temperature is noted, it must be immediately reported as per instructions contained in the IMP Handling Manual.

The Investigator (or designee) will instruct the participant to store the study medication following the instructions on the label.

Further guidance and information for the final disposition of unused study medication are provided in the IMP Handling Manual.

### **6.2.1 Drug accountability**

A Drug Accountability form will be used to record study medication dispensing and return information on a by-participant basis and will serve as source documentation during the course of the study. Details of any study medication lost, damaged (due to breakage or wastage), not used, partially used, disposed of at the study site, or returned to the Sponsor or designee must also be recorded on the appropriate forms. All supplies and pharmacy documentation must be made available throughout the study for UCB (or designee) to review.

The Investigator (or designee) is responsible for retaining all used, unused, and partially used containers of study medication until returned or destroyed.

The Investigator may assign some of the Investigator's duties for drug accountability at the study site to an appropriate pharmacist/designee.

The Investigator must ensure that the study medication is used only in accordance with the protocol.

Periodically, and/or after completion of the clinical phase of the study, all used (including empty containers)/partially used, unused, damaged, and/or expired study medication must be reconciled and either destroyed at the site according to local laws, regulations, and UCB standard operating procedures or returned to UCB (or designee). Investigational medicinal product intended for the study cannot be used for any other purpose than that described in this protocol.

### **6.3 Measures to minimize bias: randomization and blinding**

Interactive response technology (IRT) will be used for assigning eligible participants to a treatment regimen (as applicable) based on a predetermined production randomization and/or packaging schedule provided by UCB (or designee). The randomization schedule will be produced by the IRT vendor. The IRT will generate individual assignments for kits of study medication, as appropriate, according to the visit schedule.

To enroll a study participant (Visit 1), the Investigator or designee will contact the IRT and provide brief details about the participant to be enrolled. Each participant will receive a 5-digit number assigned at Screening that serves as the participant identifier throughout the study. The participant number will be required in all communication between the Investigator or designee

and the IRT regarding a particular participant. Participant numbers and kit numbers will be tracked via the IRT. Enrolled participants who withdraw from the study prior to randomization will retain their participant number without receiving a randomization number (ie, participant numbers will not be reassigned).

To randomize a participant, the Investigator or designee will contact the IRT and provide brief details about the participant to be randomized. The IRT will automatically inform the Investigator or designee of the participant's randomization number. The IRT will allocate kit numbers to the participant based on the participant number during the course of the study. The randomization number must be incorporated into the eCRF.

All participant treatment details will be allocated and maintained by the IRT. The following individuals will receive the randomization code at the start of the study:

- Designated CRO bioanalytical staff analyzing PK samples
- Sponsor clinical study supply staff
- Interactive response technology provider

The following individuals may have access to the randomization code as indicated:

- Sponsor patient safety staff as needed for reporting SAEs to regulatory authorities
- On request, members of the Data Monitoring Committee (DMC) who participate in unblinded (closed) sessions will be given information about the IMP allocation for those participants for whom data are provided at these sessions
- Unblinded CRO staff supporting preparation of the data outputs for the DMC review
- Unblinded pharmacometrics staff and statistical programmers, independent from the study team, who have access to the 12-month data for the preparation of the exposure-response analysis

To balance prognostic factors across treatment groups, randomization of study participants will be stratified using permutation blocks by gender.

In the Parkinson Progression Markers Initiative (PPMI) database, variability in MDS-UPRDS was observed to differ between male and female PD patients. Men and women also behave differently with respect to start of ST. Therefore, the study will balance treatment groups according to gender.

In the three-arm study, only participants who are recruited after the introduction of the randomization schedule which include the low-dose arm will have a chance of being assigned to low-dose UCB0599, causing a small time bias. This time bias will be considered to have no impact on how the participants respond to their assigned treatment, ie, the data collected from participants assigned to the placebo and high-dose arms prior to the introduction of the full randomization schedule will be assumed comparable to the data collected from participants assigned to the placebo and high-dose arms after the introduction of the full randomization schedule.

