## Treatment Groups and Duration

PD0053 includes a Screening Period of 3 to 6 weeks, an 18-month Treatment Period, and an SFU Period of 1 month, for a total duration of approximately 21 months. PD0053 starts with participants randomized 1:1 to either UCB0599 360mg/day or placebo. Participants will be randomized to either UCB0599 360mg/day (180mg BID), UCB0599 180mg/day (90mg BID), or placebo when the IMP for low dose UCB0599 180mg/day (90mg BID) will be available to supply sites so that the final allocation ratio is 1:1:1.

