ASYN=alpha-synuclein; CGII=Clinical Global Impression of Improvement; CGIS=Clinical Global Impression of Severity; CSF=cerebrospinal fluid; DaT-SPECT=Dopamine Transporter Imaging with Single Photon Emission Computerized Tomography; ePD=early-stage PD; EQ-5D-5L=EuroQol-5-dimension-5-level; HADS=Hospital Anxiety and Depression Scale; MDS-NMS=Movement Disorder Society-Non-motor Scale; MDS-UPDRS=Movement Disorder Society-Unified Parkinson's Disease Rating Scale; MoCA=Montreal Cognitive Assessment; PD=Parkinson's Disease; PGIC=Patient Global Impression of Change; PGIS=Patient Global Impression of Severity; PRO=Patient-Reported Outcome; RMET=restricted (t-year) mean event time; SBR=specific binding ratio; SE-ADL=Schwab and England Activities of Daily Living; ST=symptomatic treatment

Note: "In the absence of concomitant ST intake" means that all data recorded after a participant initiates ST will be censored. "Regardless of concomitant ST intake" means that participant data will be included in the analyses even after they have initiated ST. If a participant does not comply with the 12-hour ST washout prior to any visit, the data from that particular visit will be censored.

Efficacy data analysis at 12 and 18 months will take place once all participants have completed their 18-month Visit. All efficacy analyses will be carried out for the FAS and adjusted for the randomization stratification factor (ie, gender) and age at Baseline.

Treatment will be coded as a categorical variable with 3 levels (placebo, UCB0599 high dose, and UCB0599 low dose) with placebo as the reference category.

For change from Baseline analysis, treatment will be fitted as a fixed (main) effect. For longitudinal analyses of covariance and repeated measures modeling in which Baseline value is used as outcome, a treatment by time interaction will be included in this model as implicitly, the Baseline values for all groups are assumed to be equal and are reflected in the intercept of the models (Twisk, 2013).

Where applicable, explanatory continuous covariates will be mean-centered so that the intercept term can be interpreted as the expected value of the response when the dependent variables are set to their means.

Where reported alongside estimates and corresponding confidence intervals (CIs), p-values will always be presented as continuous values.

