### 10.11.3 Amendment 3 (04 Oct 2021)

#### Overall Rationale for the Amendment

PD0053 Protocol Amendment 3, dated 04 Oct 2021, was completed to add a treatment arm with a lower dose of UCB0599 180mg/day (which will come into effect with the availability of the IMP for the low dose), allow the use of historical symptomatic treatments, and to harmonize feedback from regulatory authorities and ethic review boards received during the initial Clinical Trial Applications (CTA). The following changes were implemented:

Section # and Name	Description of Change	Brief Rationale
Global	Where applicable, the wording “Study Watch” was renamed to “wearable sensor.”	To emphasize that the watch is not investigated in the clinical study. The generic term “wearable sensor” is used throughout.
Global	“Study Hub” was renamed to “Wearable Sensor Hub.”	To reflect the updates of the reference to the wearable sensor.
Global	“Device deficiencies” was replaced with “sensor deficiencies.”	To reflect the updates of the reference to the wearable sensor.
Section 1.1 Synopsis (Overall study design)	Clarification on low and high doses of UCB0599 (180mg/day and 360mg/day) was added.	To provide justification for the selected new dose arm.
Section 1.1 Synopsis (Treatment Groups and Duration)	Clarification on the wearable sensor familiarization period.	To allow start of use of the sensor in the first months of the treatment period.
Section 1.1 Synopsis (Treatment Groups and Duration)	Duration of Screening period was added.	Added for clarity.
Section 1.1 Synopsis (Number of participants)	The number of participants screened was increased.	To reflect that more participants are to be enrolled due to the additional treatment arm.

Section # and Name	Description of Change	Brief Rationale
Section 1.2 Schema	An additional dosage level was implemented to include 180mg/day (90mg BID).	To add a new lower dose treatment arm in support of dose selection for the pivotal studies.
	Change to the frequency of the DMC reviews.	To account for the increase in number of participants and to ensure regular independent review.

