Section 4.3.2 Pharmacology based dose levels	Text below Table 4-2 was updated to include observed human exposures for new dosage level 180mg/day (90mg BID).	To provide justification for the selected new dose arm.
Section 5.1 Inclusion criteria	For Canada only (already implemented in other countries): The age-related inclusion criterion #1 was updated: "Study participant must be 40 to 75 years of age inclusive."	Increase the upper age limit for inclusion in the study which reflects the early PD population. This population does not present additional risk compared to the population initially included in the study.
	Inclusion criterion #2a (previously criterion #2) was updated to add in parenthesis "(including diagnosis during Screening)."	To clarify that the PD diagnosis can be established at the time of screening for the study.

Section # and Name	Description of Change	Brief Rationale
	Inclusion criterion #4a (previously criterion #4) was revised: “A Screening DaT-SPECT, or a historical DaT-SPECT within 3 months of the Screening Visit (V1) that has been qualified by the central reader, shows evidence of dopamine transporter deficit consistent with PD as determined by a central reader.”	To allow participants with a previous DaT-SPECT that fulfills the quality criteria of the central reader and to further clarify the outcome of the readout by the central reader.
	Inclusion criterion #5a (previously criterion #5) was removed.	The inclusion criterion was deleted since genetic forms of PD are of minor incidence in the selected study population of age 40 and above.
	Inclusion criterion #6a (previously criterion #6) updated $\leq 2$ to $\leq 2.5$ modified Hoehn and Yahr staging.	To extend the study population to participants with a subtle balance issue.
	Inclusion criterion #7a (previously criterion #7) updated to include exceptions to medications for the treatment of motor symptoms of PD.	To reflect the update that participants that received short historical symptomatic treatment with an appropriate washout before trials start are allowed in the study.
Section 5.2 Exclusion criteria	Text about contacting the Medical Monitor to discuss enrollment for participants with allergies was removed from exclusion criterion #4a (previously criterion #4).	To clarify that the medical monitor is not involved in the participant selection based on feedback from the UK.

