5.1.2.3 Treatment assignment and treatment groups

Participants will be randomized in a 1:1:1 ratio to receive either UCB0599 high dose (360mg/day), UCB0599 low dose (180mg/day) or placebo. All listings and summaries will be presented by treatment group unless stated otherwise. [Appendix 4](#) outlines which summaries should present an overall summary as well as data summarized by treatment group.

Table 5–2: Treatment group descriptions

Full Description	Data Display Label
Placebo	Placebo
UCB0599 360mg/day (180mg BID)	Minzasolmin 360mg/day
UCB0599 180mg/day (90mg BID)	Minzasolmin 180mg/day
UCB0599 pooled high dose (360mg/day) and low dose (180mg/day)	Minzasolmin Total

If after unblinding it is determined that participants received treatment other than what they were randomized to, then for baseline characteristics, safety and PK analyses participants will be allocated to the treatment they predominantly received (ASPS, RS, SS and PKS assignment will be based on actual treatment). Treatment assignment for the FAS will be allocated based on randomized treatment and not actual treatment received, all efficacy analyses will be based on the FAS. A sensitivity analysis will be performed for the primary estimand where actual treatment assignment is used.

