5.3.1.3 Sensitivity analyses

The primary analysis may be repeated using additional prognostic covariates (e.g., Parkinsonian age/digital twin). The results will be part of a separate report and may not be part of the CSR.

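### Low dose vs placebo uses placebo participants randomised before the low dose was available, and no planned analysis checks that they are comparable

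*Protocol*

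**What the plan says.** Protocol 1.1 (Treatment Groups and Duration) states: "PD0053 starts with participants randomized 1:1 to either UCB0599 360mg/day or placebo". The footnote to the treatment table in Protocol 6.1 says the low dose then joins "to achieve a final randomization ratio of 1:1:1 when the IMP for low dose UCB0599 180mg/day (90mg BID) will be available to supply sites". Protocol 6.3 acknowledges that only later recruits can receive the low dose and that this creates a time bias. It continues "This time bias will be considered to have no impact on how the participants respond to their assigned treatment", and takes placebo and high-dose data from before and after the change to be comparable.

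On the analysis, the text below Table 9-1 in Protocol 9.3 says: "All efficacy analyses will be carried out for the FAS and adjusted for the randomization stratification factor (ie, gender) and age at Baseline". The categorical-time models in the SAP also include the baseline score (SAP 5.3.1.4.1). The primary slope model does not, because baseline is part of its response (SAP 5.3.1.2). Time in the models is time since baseline, not calendar time.

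Two sensitivity analyses are named for the primary estimand: an optional rerun with extra prognostic covariates (SAP 5.3.1.3), and, in SAP 5.1.2.3, "A sensitivity analysis will be performed for the primary estimand where actual treatment assignment is used". SAP 5.6 plans no subgroup analyses. The imputation and g-estimation models in SAP Appendix 5 use sex, age group, region, Part II and DaT-SPECT, but not stage.

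**The concern.** Low dose vs placebo is only partly a concurrent randomised comparison. If later participants progress more slowly than earlier ones, pooled placebo looks too steep and the low dose appears to help. If they progress faster, a real low-dose effect is masked.

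The amendment log shows how such a difference could arise, though not how large it is. Amendment 3, which added the low dose to a running study, also raised the modified Hoehn and Yahr limit from 2 to 2.5, with the reason "To extend the study population to participants with a subtle balance issue". It also allowed short past symptomatic treatment (ST) and moved Months 6, 10 and 16 into the clinic. Low-dose participants all came in under the wider criteria; some earlier placebo participants may not have. The eligibility change need not coincide with the start of three-arm randomisation.

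At stake is the low-dose estimate and its interval. These are reported for every estimand in a study meant to inform dose selection (Protocol 4.1), and SAP 2 asks readers to weigh effect sizes and confidence intervals. The stated caution covers only a positive low dose with a non-positive high dose. It would not flag a masked effect.

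**Working it through.** **Inputs.** SAP Table 3-1: intercept variance 154.0, slope variance 0.43, residual variance 31.1, placebo slope 0.90 points/month, N₁·Var(T) = 85.57, Z = 2.56. Target difference 0.27 points/month; 10% one-sided type I error; 35% data loss at 12 months; 150 randomised per arm. *Assumptions, not in the documents:* k = 20, 40 or 60 early participants in each of placebo and high dose, and a slope that differs between stages by 10% (0.09 points/month).

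**Reproducing the plan's sample size.** σ² = 154.0 + 31.1 = 185.1; ρ = 154.0/185.1 = 0.832; r = 0.43/185.1 = 0.00232; Δ = 0.27/√185.1 = 0.01985.
n = 2 × [(1 − ρ) + r × 85.57] × 2.56² / (85.57 × Δ²) = 142.7, so 143 per arm, as stated. The implied slope variance per participant is 0.793, and the SE of a slope difference at 143 per arm is √(2 × 0.793/143) = 0.105.

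**SE at 150 per arm.** Generalised least squares was run with these variance components, visits every 2 months, no loss to month 3 and then exponential loss to 35% at month 12. It gives SE 0.108, at intercept-slope correlation 0 and at 0.43. The 80% CI half-width is 1.28 × 0.108 = 0.138.

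**Bias in low dose vs placebo** = (k/150) × (slope difference between stages):

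| k | share of placebo | bias per month | % of 0.27 | in SEs | % of 80% CI half-width |
|---|---|---|---|---|---|
| 20 | 0.133 | 0.012 | 4 | 0.11 | 9 |
| 40 | 0.267 | 0.024 | 9 | 0.22 | 17 |
| 60 | 0.400 | 0.036 | 13 | 0.33 | 26 |

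Halve these for 5% drift and double them for 20%. The bias reaches 10% of target (0.027) at drifts of 0.027/(0.90 × share) = 22.5, 11 and 7.5%. On the Month 18 sum score it is 18 times larger: 0.22, 0.43 or 0.65 points, again 0.11, 0.22 or 0.33 SE.

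**In error rates** (143 per arm, SE 0.105): with one third of placebo early and 20% drift, the bias is 0.060. One-sided type I error becomes 24% instead of 10%, or power 76% instead of 90%, depending on direction. At 10% drift the figures are 16% and 84%.

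**High dose.** Allocation is 1:1 at first and 1:1:1 overall, so high dose and placebo have equal numbers in each stage. The bias is 0.000.

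**What removes the bias.** In the slope model:
- Stage as a main effect only leaves 97–99% of it.
- Stage plus stage-by-time leaves none.
- Restriction to participants randomised under the three-arm schedule leaves none.

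**Precision.** The variance ratio against the planned low-dose contrast is (1 + 150/(150 − k))/2 with concurrent placebo only, and 0.75 + 0.25 × 150/(150 − k) with stage and stage-by-time. The SE rises by 4, 9, 15% and by 2, 4, 8% respectively.

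**Limit of the stage-adjusted model.** It borrows early high-dose data. If the high-dose slope effect differed by 0.135 points/month between stages, its low-dose estimate would be off by (k/150) × 0.135/2 = 0.009, 0.018 or 0.027. The planned and concurrent-only estimates would be off by 0.000.

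**The case against.** The low dose has a secondary role. SAP 2 states the null hypothesis for high dose vs placebo only, the study is exploratory, the doses are not compared with each other, and a low-dose-only positive already carries a caution. The protocol discloses the time bias and calls it small. This limits the weight of the point but does not supply a check.

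Covariates could absorb part of a case-mix change: baseline score in the categorical models, the further covariates in Appendix 5, and prognostic covariates in the optional rerun. This is fair, and it makes the Month 18 figures closer to upper bounds if case mix is the only route. It does not reach the primary slope model, which has no baseline-score covariate, and the rerun is optional.

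The eligibility route is uncertain. Amendment 3 also added a hypokalaemia exclusion. The SAP Appendix 6 rule on past ST, applied as written, may remove some newly eligible participants from the FAS. Nothing in the documents ties Hoehn and Yahr 2.5 to a different slope.

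More ST was started than expected, so the SE is probably above 0.108. At an assumed 58–65% loss it is 0.120–0.126, and the bias at 10% drift is 0.10–0.29 SE. The bias in points is unchanged.

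Finally, SAP 1 allows supplementary analyses after database lock. A concurrent-only result chosen after unblinding would be less convincing than a prespecified one.

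**Conclusion.** The concern holds. The plan compares the low dose with placebo participants who could not have been assigned to it, assumes comparability, and includes no analysis in these documents that would test the assumption. Separate exploratory plans are mentioned but not supplied, and nothing here says they cover it.

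The size is unknown. In the scenarios above the slope bias is 4–13% of the target effect at 10% drift, in either direction, and zero without drift. These figures rest on assumed stage sizes and drift and on the Table 3-1 variance components. High dose vs placebo is unaffected. This is a low-cost improvement worth considering, not a threat to the primary evaluation.

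**What to change.** Keep the planned models as the main analysis. Before unblinding:

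1. Derive randomisation stage (two-arm or three-arm schedule) from the IRT and report counts by arm and stage.
2. For low dose vs placebo on the primary and key secondary MDS-UPDRS estimands, prespecify a sensitivity analysis restricted to participants randomised under the three-arm schedule. For the de-mediated estimands, apply the restriction in SAP 6.5.2, before bootstrapping.
3. Replace the no-impact statement in Protocol 6.3 with, for example: *The planned low dose vs placebo analysis assumes that placebo data from before and after the full schedule are comparable; this is examined against concurrently randomised placebo.*

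Optional extras:

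- For the primary slope, Part III slope and Month 18 sum score models, add stage with stage-by-time (slope) or stage-by-visit (categorical), stating that this assumes no stage-by-high-dose interaction.
- If stage is used as a covariate in Appendix 5, put it in the placebo and high-dose imputation subsets and the g-estimation models as well. In a Month 12 check, stage in the final model alone left 8.5% of the bias at 15% loss and 20% at 35% loss; g-estimation was not simulated.

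The cost is SAP wording, one derived variable and one or two extra runs per estimand. The Appendix 5 runs are the heavy ones, at 200 × 10 = 2,000 datasets per endpoint, and restriction makes the placebo and high-dose imputation subsets smaller. The loss of precision shown above applies only to the added sensitivity analyses. Main and high-dose results do not change.
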